### **10.13 Quality Control and Assurance**

The sponsor or designee will implement and maintain quality control and quality assurance procedures with written standard operating procedures to ensure that the study is conducted and data are generated, documented, and reported in compliance with the protocol, ICH GCP, and applicable regulatory requirements.

This study will be conducted in accordance with the provisions of the Declaration of Helsinki and all revisions thereof; in accordance with the ICH GCP and as required by the applicable regulatory requirements.

Necessary training for the study will be provided at the investigator's meeting and for study center personnel prior to the initiation of the study.

### **10.14 Publication and Disclosure Policy**

All information regarding S-649266 supplied by the sponsor to the investigator is privileged and confidential. The investigator agrees to use this information to accomplish the study and will not use it for other purposes without consent from the sponsor. It is understood that there is an obligation to provide the sponsor with complete data obtained during the study. The information obtained from the clinical study will be used toward the development of S-649266 and may be disclosed to regulatory authority(ies), other investigators, corporate partners, or consultants as required.

The sponsor will retain ownership of all data. All proposed publications based on the study will be subject to the sponsor's approval requirements.

The key design elements of this protocol will be posted in a publicly accessible database(s), eg, ClinicalTrials.gov, European registries, and the Japan Pharmaceutical Information Center Clinical Trial Information (JAPIC CTI).

### **10.15 Financial Disclosure**

The information on financial disclosure for investigators will be addressed in a separate agreement between the sponsor and the investigator.

## Appendix 1 Time and Events Schedule

Evaluation	Screening\Baseline	Randomization	Treatment					Test of Cure (TOC)	Follow-Up (FUP)	End of Study (EOS)
	Day -2 to Same Day Prior to Randomization a		Day 1	Day 3	Early Asses. (EA) Day 3 to 4	(Day 14) b	End of Treat. (EOT) c	EOT + 7 (± 2)	EOT + 14 (± 3)	EOT + 28 (± 3)
Rapid Diagnostic for the Presence of a Carbapenemase	X d									
Informed Consent	X									
I/E Criteria	X									
Demographics	X									
Medical History e	X									
Physical Examination	X f			X g	X g	X g	X g	X g	X g,h	
Glasgow Coma Scale	X			X	X	X	X	X		
APACHE II	X									
SOFA Score	X			X	X	X	X	X		
Clinical Assessment of Signs and/or Symptoms	X			X	X	X	X	X		
Oxygenation Status i	X			X	X	X	X	X		
Ventilator Parameters (Ventilated Patients Treated with S-649266)			X i	X i						
Chest Radiographs k (HAP/VAP/HCAP)	X			X	X	X	X	X		
CPIS Parameters (HAP/VAP/HCAP)	X			X	X	X	X	X		
Pregnancy Test l	X									

Evaluation	Screening\Baseline	Randomization	Treatment					Test of Cure (TOC)	Follow-Up (FUP)	End of Study (EOS)	
	Day -2 to Same Day Prior to Randomization a		Day 1	Day 3	Early Asses. (EA) Day 3 to 4	(Day 14) b	End of Treat. (EOT) c	EOT + 7 (± 2)	EOT + 14 (± 3)	EOT + 28 (± 3)	
Hematology Tests, Blood Chemistry Tests, and Urinalysis (Table 7-1)	X	Randomization			X	X	X	X	X	X h	
TIBC, Transferrin Iron Saturation, Hcpidin	X							X			
CrCl from Serum Creatinine m	X				X						
CrCl from Urinary Creatinine l					X						
Vital Signs n	X			X ←				X	X	X	X h
12-lead ECG	X										
Drug Administration				X ←				X			
Clinical Outcome						X	X	X	X	X	
Biologic Tissue or Fluids for Microbiologic Cultures o	X					X	X	X	X	X	
Microbiological Outcome						X	X	X	X	X	
Blood PK Samples (S-649266 Group)					X p	X p					
AE Assessment	X										X
Concomitant Therapy	X										X
Hospitalization	X										X
Vital Status	X									X	

- 
- a. If Screening and Randomization (Day 1) occur on the same day, the activities of Screening and Day 1 should be completed, without duplication of assessments.
  - b. In case treatment duration is extended beyond 14 days, an additional assessment will be conducted on Day 14.
  - c. EOT evaluations occur on the last day of study treatment. EOT can be any time after the patient had at least one dose of study treatment, duplication of assessments for a given day and EOT is not necessary.
  - d. The use of investigational diagnostics or diagnostics that are not the local standard of care for determination of carbapenem resistance will require that the investigational diagnostics section of the informed consent be signed by the patient or legally authorized representative.
  - e. Include a review of prior/concomitant therapies.
  - f. A complete physical examination including measurement of body weight and height will be performed at Screening only.
  - g. A limited physical examination relevant to the patient's current condition will be performed.
  - h. If end of study evaluation is by phone, physical examination, laboratory tests, and vital signs will not be performed.
  - i. Patients receiving an oxygen inhalation treatment.
  - j. For ventilated patients treated with S-649266, specified ventilator parameters will be captured at the start of the infusion (acceptable time window; 0 hours to end of infusion) which PK sampling will be taken.
  - k. **At German sites**, in sites where chest radiographs after screening are part of the standard of care, ie, a chest radiograph is clinically indicated by the treating physicians, it can be performed as usual without a special informed consent. If a chest radiograph is not standard of care (no clinical indication), and is planned based on the study protocol, an informed consent from a conscious patient is mandatory. Chest radiographs without clinical indication cannot be performed in unconscious patients.
  - l. Urine or serum pregnancy test only for females who are not diagnosed as postmenopausal or surgically sterile.
  - m. The CrCl (the Cockcroft-Gault equation) and eGFR (the MDRD equation) will be calculated from the serum creatinine. For patients with eGFR  $\geq$  90 mL/min/1.73 m^2 at baseline, urine samples will be collected a time interval as short as 2 hours or up to 8 hours.
  - n. Blood pressure (systolic/diastolic pressures), body temperature, pulse rate, and respiratory rate.
  - o. Biologic tissue or fluids (including blood regardless of the infection site) for microbiologic cultures will be obtained with 48 hours of the start of treatment, and at specified times and at the investigator's discretion. Two blood samples from separate venipunctures will be collected within 48 hours prior to start of the first dose of study treatment. Subsequent blood cultures are to be completed only if the first culture is positive.
  - p. PK blood samples will be drawn on Day 3 after at least the sixth dose of study drug; one draw just prior to the infusion of the dose, 1 hour after start of infusion, at the end of infusion, and at 1 hour after the end of infusion. Patients with non-stable renal function resulting in a dosage adjustment at EA will undergo another blood PK sampling (4 samples at the above specified timepoints) within 24 to 72 hours after their dosing adjustment. If possible, a single blood draw should be performed as soon as possible at EOT in case of premature EOT.

## **Appendix 2      SIRS Criteria**

Patient exhibits 2 or more of the following responses:

1. Temperature greater than 38°C (100.4°F) or less than 36°C (96.8°F)
2. Heart rate greater than 90 beats/minute
3. Respiratory rate greater than or equal to 20 breaths/minute or PaCO2 less than 32 mmHg
4. WBC greater than 12,000/mm^3 or less than 4000/mm^3 or > 10% immature (band) forms

## Appendix 3 European Medicines Agency Completes Review of Polymyxin-based Medicines

### Information to Healthcare Professionals

The recommendations of European Medicines Agency (EMA) are based on a review of the available clinical, pharmacological, and pharmacokinetic data, although significant gaps still exist, particularly with regard to the pharmacokinetics in special populations such as children and patients with renal impairment. Research currently underway may provide further information on pharmacodynamics and pharmacokinetics of these medicines to improve the evidence-base behind any dose recommendations. However, it was considered that in the interim the product information should be updated throughout the EU to reflect what was currently known.

- Doses should always be expressed in IU of colistimethate sodium. To address the differences in the way in which the strength of colistimethate sodium and colistin are expressed in the EU and in other regions such as the USA and Australia, which has led to errors in reporting in the medical literature and could potentially lead to serious medication errors, the following table has been recommended for inclusion in product information:

Colistimethate sodium (IU)	Colistimethate sodium (mg)	Colistin-base activity (CBA) (mg) 
12,500	1	0.4
150,000	12	5
1,000,000	80	34
4,500,000	360	150
9,000,000	720	300

 Based on a nominal potency of the drug substance of 12,500 IU/mg or 0.424 mg CBA/mg; both IU and mg CBA are expressions of potency and have only approximate relation to the mass of drug substance.

- Intravenous colistimethate sodium is indicated in adults and children including neonates for the treatment of serious infections due to aerobic Gram-negative pathogens in patients with limited treatment options. Consideration should be given to coadministration with another antibacterial agent whenever this is possible.
- Dosage should be in line with relevant treatment guidelines. Based on the limited available evidence the recommended dose in adults is 9 million IU daily in 2 or 3 divided doses as a slow intravenous infusion; in critically ill patients, a loading dose of 9 million IU should be given. Doses should be reduced according to creatinine clearance in patients with renal impairment.
- Intravenous colistimethate sodium does not cross the blood-brain barrier to a significant extent. Where appropriate, adult doses of 125,000 IU for intraventricular administration and no more than this for intrathecal administration are recommended.

- Use of intravenous colistimethate sodium together with other medications that are potentially nephrotoxic or neurotoxic should be undertaken with great caution.

## **Appendix 4      Microbiology Tests**

Appropriate clinical specimens will be obtained from all patients within 48 hours prior to the start of the infusion of the first dose of study treatment therapy. Biologic tissue or fluids for microbiologic cultures will be sent to the local laboratory for identification of all pathogens causing the infection. Two blood samples from separate venipunctures will be obtained from all patients and sent to the local laboratory. After initiation of study treatment, appropriate clinical specimens including blood culture will be obtained at the specified evaluation points (Appendix 1).

Identified isolates in unscheduled cultures should be sent to the central lab.

In general, all specimens should also have Gram stain of infected material (not swab). A report of both inflammatory cells and bacteria is necessary.

Inappropriate clinical specimens should not be used for confirmatory culture identification of causative pathogens.

### **1. HAP/VAP/HCAP Specific Procedures**

Patients enrolled in a HAP/VAP/HCAP study should have a baseline respiratory specimen obtained for Gram stain and culture [1]. In addition to defining the bacterial etiology for HAP/VAP/HCAP, the Gram stain and culture are important considerations because they may be used to define analysis populations and to characterize the quality and findings of the respiratory specimen sent for culture. More specifically, the low-power microscopic view of the Gram stain can be used to ascertain the quality of the respiratory specimen, which helps to ensure that the respiratory specimen sent for culture does not represent oropharyngeal contamination (eg, fewer than 10 squamous epithelial cells and greater than 25 neutrophils is an example of an adequate expectorated sputum specimen). The high power microscopic view of the Gram stain can be used to characterize the general type of bacteria causing the pneumonia (eg, a Gram-positive or a Gram-negative bacterial pathogen). When bacterial growth is obtained on culture of the respiratory specimen, in vitro susceptibility tests should be performed by using standardized methods unless otherwise justified.

Endobronchial culture specimens collected by BAL or protected specimen brush (PSB) should be grown quantitatively with appropriate method specific dilutions.

### **2. cUTI Specific Procedures**

**Clean-Catch Mid-Stream Urine Specimen:** After appropriate patient preparation, a specimen should be collected and immediately sent to the microbiology laboratory or properly stored for no longer than 24 hours.

**Urine Specimen from Patients with Indwelling Urinary Catheters:** Because biofilms on indwelling catheters (eg, Foley catheters) are more likely to be present after the catheter has been in place for a period of time, samples should be collected following the placement of a new catheter. If the placement of a new catheter is contraindicated or is

not feasible, specimens should be collected using aseptic techniques with the urine obtained through a properly disinfected collection port. Urine samples should never be obtained from the collection bag.

Urine Evaluations: A microscopic evaluation (eg, Gram stain) or dipstick analysis for leukocytes, nitrates, or a catalase test should be performed and the specimen cultured. In general, bacteria identified at  $1 \times 10^5$  CFU/mL or greater should be considered a bacterial pathogen (probability of true pathogen is greater than that of contamination). Quantitative urine culture by appropriate methods should be performed using a calibrated loop that would identify bacteria at a lower limit of  $10^3$  CFU/mL. In vitro antibiotic susceptibility testing of the isolates to the investigational drug and to other antibiotic drugs that may be used to treat cUTIs should be performed using standardized methods unless otherwise justified.

If possible, the identity of bacteria that are demonstrated in culture between  $10^3$  CFU/mL and  $10^4$  CFU/mL should be determined as these may be background bacteria associated with the method of collection.

### **3. Bloodstream and Sepsis Infections: Specific Procedures**

For infections categorized as BSI/sepsis, the following guidelines are provided (for details see reference infectious disease society of America/ American society for microbiology (IDSA/ASM) guidelines [2]). These guidelines apply to blood cultures and infection site tissue or fluids cultures for patients with infections other than HAP/VAP/HCAP or cUTI.

## Culture Procedures

Infection Site	Culture Method (Gram Stain Required for All Cultures or Appropriate Specimen)
Blood Stream Infection (Bacteremia)	
Primary (Not Endocarditis)	2-3 separate “sets” of blood cultures (10 mL/bottle) drawn from peripheral vein
Secondary	2-3 separate “sets” of blood cultures (10 mL/bottle) drawn from peripheral vein
Line Related	2-3 separate “sets” of blood cultures (10 mL/bottle) drawn from peripheral vein
Skin/Skin Structure Infections	
Primary Skin Infection (eg, Necrotizing Fasciitis)	Quantitative, semi-quantitative tissue culture (not swab)
Burn Wound Infection	Quantitative, semi-quantitative tissue culture (not swab)
Human/Animal Bite Infection	Tissue culture or aspirate (not swab)
Surgical Site Infection	Tissue culture or aspirate (not swab)
Trauma Associated Skin Infection	Post debridement tissue culture or aspirate (not swab)
Intra-Abdominal Infections	
Spontaneous Bacterial Peritonitis	Culture aspirate or inoculate blood culture bottle
Tertiary Peritonitis (Post-Surgical)	Fluid aspirate or tissue culture
Abscess of Liver	Lesion aspirate
Biliary Tract Infection	Lesion aspirate
Secondary Pancreatic Infection	Lesion aspirate
Respiratory Tract other than HAP/VAP/HCAP	
Community Acquired Pneumonia	Expectorated sputum, or bronchoscopic specimen
Lung Abscess	Lesion aspirate or bronchoscopic specimen
Pleural Space, Empyema	Culture aspirate or inoculate blood culture bottle
Pelvic Infection (Post-Surgical)	Fluid aspirate or tissue culture

## Appendix 5 Glasgow Coma Scale

Eye Opening	Spontaneous	4
	To speech	3
	To pain	2
	None	1
Best Verbal Response	Orientated	5
	Confused	4
	Words	3
	Sounds	2
	None	1
Best Motor Response	Obey commands	6
	Localising	5
	Normal flexion	4
	Flexing	3
	Extension	2
	None	1

## Appendix 6 APACHE II Score

### The APACHE II Severity of Disease Classification System

Physiologic Variable	High Abnormal Range					Low Abnormal Range			
	+4	+3	+2	+1	0	+1	+2	+3	+4
Temperature - Rectal (°C)	≥41	39 to 40.9		38.5 to 38.9	36 to 38.4	34 to 35.9	32 to 33.9	30 to 31.9	≤29.9
Mean Arterial Pressure - mm Hg	≥160	130 to 159	110 to 129		70 to 109		50 to 69		≤49
Heart Rate (ventricular response)	≥180	140 to 179	110 to 139		70 to 109		55 to 69	40 to 54	≤39
Respiratory Rate (non-ventilated or ventilated)	≥50	35 to 49		25 to 34	12 to 24	10 to 11	6 to 9		≤5
Oxygenation: A-aDO 2 or PaO 2 (mm Hg)									
a. FIO 2 ≥0.5 record A-aDO 2	≥500	350 to 499	200 to 349		<200				
b. FIO 2 <0.5 record PaO 2					>70	61 to 70		55 to 60	<55
Arterial pH (preferred) OR	≥7.7	7.6 to 7.69		7.5 to 7.59	7.33 to 7.49		7.25 to 7.32	7.15 to 7.24	<7.15
Serum HCO 3 (venous mEq/L) (not preferred, but may use if no ABGs)	≥52	41 to 51.9		32 to 40.9	22 to 31.9		18 to 21.9	15 to 17.9	<15
Serum Sodium (mEq/L)	≥180	160 to 179	155 to 159	150 to 154	130 to 149		120 to 129	111 to 119	≤110
Serum Potassium (mEq/L)	≥7	6 to 6.9		5.5 to 5.9	3.5 to 5.4	3 to 3.4	2.5 to 2.9		<2.5
Serum Creatinine (mg/dL) Double point score for acute renal failure	≥3.5	2 to 3.4	1.5 to 1.9		0.6 to 1.4		<0.6		
Hematocrit (%)	≥60		50 to 59.9	46 to 49.9	30 to 45.9		20 to 29.9		<20
White Blood Cell Count (total/mm  ) (in 1000s)	≥40		20 to 39.9	15 to 19.9	3 to 14.9		1 to 2.9		<1
Glasgow Coma Score (GCS)	Score = 15 minus actual GCS								
A. Total Acute Physiology Score (sum of 12 above points)									
B. Age points (years) <44=0; 45 to 54=2; 55 to 64=3; 65 to 74=5; ≥75=6									
C. Chronic Health Points (see below)									
Total APACHE II Score (add together the points from A+B+C)									

Chronic Health Points: If the patient has a history of severe organ system insufficiency or is immunocompromised as defined below, assign points as follows: 5 points for nonoperative or emergency postoperative patients and 2 points for elective postoperative patients.

---

**Definitions:** organ insufficiency or immunocompromised state must have been evident **prior** to this hospital admission and conform to the following criteria:

- **Liver** – biopsy proven cirrhosis and documented portal hypertension; episodes of past upper gastrointestinal (GI) bleeding attributed to portal hypertension; or prior episodes of hepatic failure/encephalopathy/coma.
- **Cardiovascular** – New York Heart Association Class IV.
- **Respiratory** – Chronic restrictive, obstructive, or vascular disease resulting in severe exercise restriction (ie, unable to climb stairs or perform household duties; or documented chronic hypoxia, hypercapnia, secondary polycythemia, severe pulmonary hypertension (> 40 mm Hg), or respirator dependency.
- **Renal** – receiving chronic dialysis.
- **Immunocompromised** – the patient has received therapy that suppresses resistance to infection (eg, immunosuppression, chemotherapy, radiation, long term or recent high dose steroids, or has a disease that is sufficiently advanced to suppress resistance to infection, eg, leukemia, lymphoma, AIDS).

## Appendix 7 SOFA Score

The Sequential Organ Failure Assessment (SOFA) Score*					
Variables	SOFA Score				
	0	1	2	3	4
Respiration PaO 2 /FiO 2 , mm Hg	> 400	≤ 400	≤ 300	≤ 200 †	≤ 100 †
Coagulation Platelets ×10  /μL	> 150	≤ 150	≤ 100	≤ 50	≤ 20
Liver Bilirubin, mg/dL‡	< 1.2	1.2 – 1.9	2.0 – 5.9	6.0 – 11.9	> 12.0
Cardiovascular Hypotension	No hypotension	Mean arterial pressure < 70 mmHg	Dop ≤ 5 or dob (any dose) §	Dop > 5, epi ≤ 0.1, or norepi ≤ 0.1 §	Dop > 15, epi > 0.1, or norepi > 0.1 §
Central Nervous System Glasgow Coma Scale	15	13 - 14	10 - 12	6 - 9	< 6
Renal Creatinine, mg/dL or Urine Output, mL/d 	< 1.2	1.2 – 1.9	2.0 – 3.4	3.5 – 4.9 or < 500	> 5.0 or < 200

\* Norepi indicates norepinephrine; dob, dobutamine; Dop, dopamine; epi, epinephrine; and FiO2, fraction of inspired oxygen.

† Values are with respiratory support.

‡ To convert bilirubin from mg/dL to μmol/L, multiply by 17.1.

§ Adrenergic agents administered for at least 1 hour (doses given are in μg/kg/minute).

|| To convert creatinine from mg/dL to μmol/L, multiply by 88.4

## Appendix 8 Clinical Pulmonary Infection Score (CPIS) Parameters

CPIS Points	0	1	2
Tracheal Secretions*	Few	Moderate	Large
Chest X-Ray Infiltrates†	None	Patchy or diffuse	Localized
Temperature (°C)	≥ 36.1 and ≤ 38.4	≥ 38.5 and ≤ 38.9	≥ 39.0 or ≤ 36.0
Leukocytes (/mm  ) †	≥ 4000 and ≤ 11,000	< 4000 or > 11,000	
PaO 2 /FiO 2 (mmHg)‡	> 240 or evidence of Acute Respiratory Distress Syndrome (ARDS)		≤ 240 and no evidence of ARDS

\* If purulent: +1

† For post baseline CPI scores where the radiograph or leukocytosis has improved: -1

‡ Use first blood gas measure in morning. For non-ventilated patients who, based on local practice, do not have blood gasses done, a PaO2/FiO2 point value of zero may be assigned.

## **Appendix 9            Management Criteria for Abnormal Liver Function Tests**

Management Criteria for Abnormal Liver Function tests have been designed to ensure patient safety and evaluate liver event etiology.

### **Abnormal Liver Chemistry Criteria:**

The investigator or sub-investigator must review study patient laboratories to identify if any levels meet the following criteria a.-e.:

- a. AST or ALT  $> 5 \times$  ULN (if baseline ALT is  $\leq$  ULN);
- b. AST or ALT  $> 8 \times$  ULN;
- c. AST or ALT  $> 3 \times$  ULN and total bilirubin (TBL)  $> 2 \times$  ULN or PT-INR  $> 1.5$ , if PT-INR measured;
- d. AST or ALT  $> 3 \times$  ULN (if baseline ALT is  $\leq$  ULN) with signs or symptoms compatible with hepatitis or hypersensitivity (eg, fatigue, nausea, vomiting, right upper quadrant pain or tenderness, jaundice, fever, rash or eosinophilia [ $> 5\%$ ]),  
OR
- e. AST or ALT  $> 3 \times$  increase from baseline ALT with signs or symptoms compatible with hepatitis or hypersensitivity (eg, fatigue, nausea, vomiting, right upper quadrant pain or tenderness, jaundice, fever, rash or eosinophilia [ $> 5\%$ ]);

Patients who develop AST or ALT  $> 5 \times$  ULN (if baseline ALT is  $>$  ULN) should be followed weekly until resolution or stabilization.

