**Safety Assessments:**

Patient safety will be assessed daily from the time of informed consent, while the patient is hospitalized, and through to EOS by the identification of adverse events (AEs). Adverse events defined as new or worsening symptoms since the time of Randomization will be used to determine the safety of the study treatment. In case treatment duration is extended beyond 14 days, additional safety assessments will be conducted on Day 14. Safety surveillance will extend to up to 28 days after the last dose of the study drug. Clinical laboratory tests of blood chemistry, hematology, and urinalysis will be performed at Screening, EA, EOT, TOC, and FUP. In addition, an electrocardiograph (ECG) will be performed at Screening/baseline. Vital signs including body temperature and AEs will be recorded daily.

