#### **7.8.1.5 Clinical Assessment of Signs and/or Symptoms**

General signs and/or symptoms of infection, including fatigue, chills/rigors, malaise, nausea, vomiting will be assessed at baseline as absent, mild, moderate, severe, or unknown. Signs and symptoms present at baseline will similarly be assessed at the specified subsequent evaluation points. Any new sign or symptom of the underlying infection which may occur in any specific patient during the course of the study will also be assessed. The results will be entered in the eCRF.

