### **7.12.6 Clinical Laboratory Adverse Events**

For any abnormal laboratory test results (hematology, blood chemistry, or urinalysis) or other safety assessments (eg, physical examination, vital signs, ECG) that are worsening from baseline or occur thereafter in the course of the study, the investigator or sub-investigator will consider whether these results are clinically significant. Abnormal laboratory test results are defined as values outside the reference range. Any test results which are considered to be clinically significant by the investigator or sub-investigator are to be recorded as AEs. If an abnormal laboratory finding is associated with disease or organ toxicity, the investigator should report only the disease or organ toxicity as AEs. These AEs should also be assessed as to whether they meet the definition of seriousness and reported accordingly.

The investigator or sub-investigator will consider test results to be clinically significant in the following circumstances:

- Test result leads to any of the outcomes included in the definition of an SAE.
- Test result leads to discontinuation from the study.
- Test result leads to a concomitant drug treatment or other therapy.
- Test result requires additional diagnostic testing or other medical intervention.
- Test result meets the management criteria for liver function abnormalities identified in Appendix 9.

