### **Action to Be Taken by Investigator:**

If any one of abnormal liver chemistry criteria is met, the investigator or sub-investigator must do the following:

- Following the initial observed elevation, every effort should be made to have the patient reassessed within 48 to 72 hours to repeat liver function chemistries and for further hepatic evaluation.
- Patients must be monitored 2 to 3 times per week until liver function chemistries (ALT, AST, ALP, total bilirubin) resolve, stabilize or return to within the normal range or to baseline levels.
- This event must be reported to the sponsor within 48 to 72 hours of learning after its occurrence on the Liver Event Form.
- Consultation with a specialist such as a hepatologist is considered.
- Liver imaging (ie, ultrasound, magnetic resonance imaging [MRI], computerized tomography (CT) is considered.

- For criteria c, termed “Hy’s law,” the case must be reported as an SAE (if baseline AST or ALT is  $\leq$  ULN).  
If baseline AST or ALT is  $>$  ULN, the case that meets the following criteria must be reported as an SAE.  
AST or ALT  $>$  3  $\times$  increase from baseline AST or ALT and TBL  $>$  2  $\times$  increase from baseline TBL

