### **Follow-up Examination:**

If any of abnormal liver chemistry criteria are met, the following assessments should be obtained at FUP and documented in the Liver Event Form:

- Clinical signs and symptoms course
- Concomitant medications: OTC/herbal/dietary supplements (start and stop dates)
- Alcohol use
- Risk factors for nonalcoholic steatohepatitis (NASH) such as diabetes, obesity and hypertriglyceridemia
- Autoimmune hepatitis/cholangitis
- Wilson's disease
- Laboratory Assessments
  - Viral hepatitis serology
    - Hepatitis A IgM antibody
    - Hepatitis B surface antigen and Hepatitis B core antibody (IgM)
    - Hepatitis C RNA
    - Hepatitis E IgM antibody
    - Cytomegalovirus IgM antibody
    - Epstein-Barr viral capsid antigen IgM antibody

For patients with total bilirubin of  $>$  1.5 ULN, conjugated bilirubin should be measured

Complete blood count with differential

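### Protocol Appendix 9 judges AST by baseline ALT, so a symptomatic AST rise to as much as 5 × ULN can meet no liver trigger

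*Protocol*

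**What the plan says.** Appendix 9 of the protocol sets five criteria and one weaker follow-up rule, all worded for AST or ALT:

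| Statement | Level of AST or ALT | Baseline reference | Further condition |
|---|---|---|---|
| a | > 5 × ULN | baseline ALT ≤ ULN | none |
| b | > 8 × ULN | none | none |
| c | > 3 × ULN | none | bilirubin > 2 × ULN or PT-INR > 1.5 |
| d | > 3 × ULN | baseline ALT ≤ ULN | symptoms |
| e | more than threefold | measured from baseline ALT | symptoms |
| weekly rule | > 5 × ULN | baseline ALT > ULN | none |

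The condition in a and d reads "ULN (if baseline ALT is" at or below ULN. Criterion e is an "increase from baseline ALT with signs or symptoms compatible with hepatitis or hypersensitivity". Patients under the weekly rule "should be followed weekly until resolution or stabilization".

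If any of a to e is met, "every effort should be made to have the patient reassessed within 48 to 72 hours to repeat liver function chemistries". The patient is then monitored two to three times a week and the event goes to the sponsor on the Liver Event Form. In addition, "the following assessments should be obtained at FUP and documented in the Liver Event Form"; these include viral hepatitis serology. Section 7.12.6 makes meeting Appendix 9 one ground for calling a result clinically significant, and hence an AE: "Test result meets the management criteria for liver function abnormalities identified in Appendix 9".

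Baseline AST appears nowhere in the criteria list. The SAE paragraph later in the same appendix does refer to baseline AST or ALT.

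**The concern.** A raised baseline ALT says little about whether a later AST rise is new. As written, though, it switches off a and d for AST and moves the AST level needed for e, even when AST was normal at entry. No other section supplies an AST trigger tied to baseline AST, and no reason is given for using ALT alone. Section 4.3 sets no AST or ALT limit, so these patients are eligible.

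Without a trigger there is no mandatory retest within 48 to 72 hours, closer monitoring, Liver Event Form or aetiology work-up. The patient falls back on the visit schedule: "Clinical laboratory tests of blood chemistry, hematology, and urinalysis will be performed at Screening, EA, EOT, TOC, and FUP". Nor is the symptom condition in d and e a rare event here. Fatigue, nausea and vomiting count as compatible with hepatitis, and section 7.8.1.5 rates the same symptoms as part of the infection: "General signs and/or symptoms of infection, including fatigue, chills/rigors, malaise, nausea, vomiting will be assessed at baseline".

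**Working it through.** The plan gives no figure to reproduce, so the check applies the rules to a worked patient. The patient values are assumptions; the thresholds are those of Appendix 9.

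**Inputs (assumed).** ULN 40 U/L for both enzymes; baseline AST 30 and ALT 70; ALT stays at 70; bilirubin and INR normal, so c is not met.

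**Two readings of e.** A more than threefold increase may mean a value above 3 × baseline, or a rise of more than 3 × baseline (a value above 4 × baseline). Both were used.

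**Thresholds for AST with symptoms**

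| Statement | As written (baseline ALT 70) | Own baseline (AST 30) |
|---|---|---|
| a | off, 70 > 40 | > 5 × 40 = 200 |
| b | > 8 × 40 = 320 | > 320 |
| d | off, 70 > 40 | > 3 × 40 = 120 |
| e, value reading | > 3 × 70 = 210 | > 3 × 30 = 90 |
| e, rise reading | > 4 × 70 = 280 | > 4 × 30 = 120 |
| weekly rule | > 5 × 40 = 200 | off, 30 ≤ 40 |

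**With symptoms.** AST 121–200 meets nothing as written, under either reading of e, but meets d on its own baseline. AST 180 is an example: 180/30 = 6-fold and 180/40 = 4.5 × ULN. From 201 to 210 (value reading) or 201 to 280 (rise reading) only weekly follow-up applies.

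**Without symptoms.** AST 201–320 gets weekly follow-up only, where its own baseline would give criterion a.

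**Sensitivity.** Symptomatic AST that meets nothing as written but meets d on its own baseline:

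| Assumption varied | Value reading | Rise reading |
|---|---|---|
| ULN 30 (baselines 30/70) | 91–150 | 91–150 |
| ULN 35 | 106–175 | 106–175 |
| ULN 45 | 136–210 | 136–225 |
| ULN 50 | 151–210 | 151–250 |
| Baseline ALT 45 (ULN 40) | 121–135 | 121–180 |
| Baseline ALT 50 | 121–150 | 121–200 |
| Baseline ALT 60 | 121–180 | 121–200 |
| Baseline ALT 70 or more | 121–200 | 121–200 |

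**Check in multiples of ULN.** Take baseline AST 0.8 and ALT 2.0 × ULN with symptomatic AST 4.9 × ULN, a 4.9/0.8 = 6.1-fold rise. Criteria a and d are off; b needs more than 8, e more than 3 × 2 = 6 (or 4 × 2 = 8), and the weekly rule more than 5. Nothing is met. With baseline ALT at 1.0 × ULN the same AST meets d and e. On the value reading, the highest AST that meets nothing is 3.6 × ULN at baseline ALT 1.2, 4.5 at 1.5, and 5.0 at 1.67 or above. On the rise reading it is 4.8 at 1.2, and 5.0 at 1.5 or above. With AST judged by its own baseline of 0.8, it falls to 3 × 0.8 = 2.4 × ULN on the value reading. On the rise reading it is 3.0 × ULN, where d takes over.

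**Time to the next required chemistry.** EA is on Day 3 or 4 and treatment lasts 7 to 14 days. The gap from EA to EOT is therefore 7 − 4 = 3 to 14 − 3 = 11 days. TOC is EOT + 7 ± 2 days, so 5 to 9 days after EOT.

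**The case against.** The strongest reply is that the gap is bounded and the case narrow. Nothing in Appendix 9 is met only up to 5 × ULN, with bilirubin at most 2 × ULN and INR at most 1.5; above that come the weekly rule and then b. The patient must have discordant baselines and a sharp AST rise while ALT stays put; if ALT also climbs, e can fire on ALT. All of this stands.

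Second, other safeguards exist. Treatment is given in hospital, clinical status is reviewed daily and a DSMB reviews patient data. Section 7.12.6 lets the investigator call a worsening result clinically significant on other grounds, such as needing further testing. SAP Table 10-1 counts AST by multiples of ULN whatever the baseline. These limit the harm, but none of them requires the early retest, the Liver Event Form or the work-up. The follow-up of abnormal results in section 8.5 concerns EOS tests and continuing changes, not the early retest. The 3-day minimum gap can also be shorter: 7 − 5 = 2 days if EA uses its one-day window, and less still in the 5-day cUTI course. That does not alter the upper end.

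Third, judging each enzyme by its own baseline removes triggers elsewhere. Take baseline AST 70, ALT 30 and ULN 40 (bilirubin and INR normal). Symptomatic AST 91–200 (121–200 on the rise reading) goes from a trigger to none, and 201–210 (201–280) to weekly follow-up. Without symptoms, 201–320 moves from criterion a to weekly follow-up. This cost is real. Part of it is the loss of spurious alarms: on the value reading, AST 91 from a baseline of 70 (91/70 = 1.3-fold) now meets e. The remainder matches how the appendix already treats ALT when baseline ALT is raised.

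**Conclusion.** The concern holds. Appendix 9 measures AST against the wrong enzyme's baseline in criteria a, d and e and in the weekly rule, and it misfires in both directions. In the worked patient, symptomatic AST from 121 to 200 U/L (above 3 and up to 5 × ULN) sets off nothing in the appendix. Between 201 and 320 without symptoms, weekly follow-up replaces criterion a. The exact bands depend on the assumed ULN and baselines, on stable ALT, and on normal bilirubin and INR; the logic does not. How many of the roughly 150 patients would have such baselines cannot be told from the documents. No efficacy result is affected, and the loss is of a mandatory safety trigger rather than of all detection. It should be corrected.

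**What to change.** In criteria a, d and e and in the weekly sentence, judge AST against baseline AST and ALT against baseline ALT, leaving every threshold as it is. Leave the SAE paragraph alone: its wording already names both enzymes, and any overlap errs towards reporting. Optionally, state whether the threefold increase in e is the value reached or the rise.

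The cost is a wording amendment that needs written IRB/IEC approval (section 10.10) at about 100 planned sites, so it is best bundled with another amendment. No new data are needed, because AST is already measured at Screening (Table 7-1). If the sponsor will not accept losing any present trigger, the own-baseline rule could be added alongside the current one, at the price of keeping the spurious alarms.
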